**SfE CORE Study Protocol**

		Relevant Laboratory Results: HbA1c if has diabetes.	months until leaves clinic.
Exploratory	
Demographic and clinical characteristics of people attending clinics.
 
To look at changes in weight and well-being over a year and whether this is affected by treatment modality
 
To explore potential disparities in access to specialist weight management service based on demographic factors (e.g., ethnicity, socioeconomic status).
 
To explore potential disparities in outcomes from specialist weight management service based on demographic factors (e.g., ethnicity, socioeconomic status).
 
To explore the outcomes and data collection within primary care additional to specialist weight management services.
	
All key measures mentioned above
 
Changes in Weight and Wellbeing - Weight, BMI, EQ5D and Body Q scores changes over 12 months. Comparison of these changes between different treatment modalities.
 
Access Disparities: Assess whether certain demographic groups are underrepresented in specialist weight management services
 
Outcome Disparities: Analyse differences in clinical outcomes across various demographic subgroups
 
Expectation: building for the future with expectations of services potentially moving from secondary/tertiary care to primary care sites especially in the role of GLP1 treatments
	
Baseline
 
Baseline and every 12 months.
 
Baseline and every 12 months.
 
Baseline and every 12 months.

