#### SfE CORE Study Protocol

2. For the centres entering data to capture data on 60% of the patients attending their clinics.
3. To compare the data entered by 100 patients to that collected by a doctor in their initial interview. This will validate that data entry by patients is reliable.
4. To demonstrate that key outcomes are captured in sufficient quantity to give a fair representation of the people attending the clinics.
5. To describe the demographics and clinical characteristics of people attending the specialist weight management services who sign up to the study.
6. To look at changes in weight and well-being over the time in clinic and whether this is affected by treatment modality.
7. To explore potential disparities in access to specialist weight management services based on demographic factors (e.g., ethnicity, socioeconomic status).
8. To explore potential disparities in outcomes from specialist weight management services based on demographic factors (e.g., ethnicity, socioeconomic status).
9. To explore this methodology in collecting data on these characteristics from those patients who attend weight management services in primary care settings.

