### 3.2 Outcomes

	Objectives	Outcome Measures	Timepoint(s)
Primary	To demonstrate that our system can be integrated into specialist weight management services clinics and collect data on patients attending clinics.	The number of clinics using the system by end of year 2 of the project. Our aim would be to have 50% of specialist weight management services using this system.	24 months
Secondary	To demonstrate that key outcomes are captured in sufficient quantity to give a fair representation of the people attending the clinics	That the clinics on average are collecting data on 60% of the patients that attend their clinics and on these they have at least 80% data on our key outcomes which are  Demographics Age, sex, socioeconomic status, ethnicity, marital status and employment status and Job.	Baseline  Baseline

SfE CORE Study Protocol

		
Weight history Birth weight, age weight problem started at, highest and lowest weight. Current weight.
 
Previous Weight Loss Attempts Previous Bariatric surgery – Y/N – if Y when and Type. Attempts at commercial diets – Y/N if Y when and Type Tried weight loss medication – Y/N if Y when and Type
 
Medical and drug history List of medical problems with date started. List of drugs taking with dose, frequency and start date.
 
Clinical Treatments Diet and Exercise advice Y/N if yes details and date offered Low calorie diet Y/N if yes details and date started and finished. Specific help with eating habits Y/N, If yes details and date (S) delivered Sessions with psychologist Y/N, If yes details and date (s) delivered. Weight loss drugs Y/N if yes which type and when started. Referred for surgery Y/N if yes when.
 
Patient-Reported Outcomes EQ5D and Body Q
 
Clinical Measures Weight, height, BMI, blood pressure.
	
Baseline
 
Baseline and every 12 months until leaves clinic.
 
Baseline and every 12 months until leaves clinic.
 
Baseline and every 12 months until leaves clinic.
 
Baseline and every 12 months until leaves clinic.
 
Baseline and every 12 months until leaves clinic.
 
Baseline and every 12 months until leaves clinic.

--	--	---	---

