#### SfE CORE Study Protocol

engage more in their health care by using the entirety of the app.		
EQ5D and Body Q questionnaire will be available for the patient to complete		Every 3 months patients will be prompted to update their information
Patient support groups pertinent to the care of these patients will be highlighted on a separate tab in the app		

Data from clinic appointments will be entered by healthcare professionals or those with delegated access per site. These people will check the data that the patient has put in and correct if mistakes have been made. In addition, they will enter weight, height and blood pressure readings from the clinic appointments, HbA1c if measured and details on any treatments offered. Finally, they will assess the severity of the patient's medical health using the Kings and Edmonton scores and record this on the *PeopleWith* dashboard. This data entry will be repeated after each clinical visit.

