#### Data analysis

The primary outcome of this study is the number of clinics collecting data. Our aim is to get 50% of specialist weight management service using the database. We will report the number of specialist weight management service and what percentage of clinics are using the app at year 2 of the project.

The secondary outcomes of this study are the percentage of patients who we capture data on, and the percentage of data captured on key variables. Our aim to capture data on 60% of patients who attend the services and of those who sign up to the study aim to capture key data on 80% of these patients. The percentage of people we capture the data on will be = (the number of people we have data on/the number of people who attend the clinic) X 100. The percentage of key variable will be worked out for each variable and will be = (number of variable entered/ number of variable possible) x 100.

For the exploratory analysis we will use simple stats (mean, median, SD, interquartile ranges and percentage) to describe the demographic and clinical characteristics of the people entered into the database. Multivariable linear regression will be used to look at the change in weight, BMI, EQ5D and Body Q scores over 12 months and to determine if this is influenced by treatment modality and demographic groups. All analysis will be done in STATA.

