### **10.2 Appendix 2 – Schedule of Procedures**

Timepoint	Event
Baseline	Informed Consent, Clinical Data Collected, Questionnaires (EQ5D and BODYQ) via Patient app, clinical data collected
Every 12 months until exit of clinic or study ends	Clinical Data Collected, Questionnaires (EQ5D and BODYQ) via Patient app
Triggered patient data collection	Upon notification every 3 months, patients will be invited to update treatments and symptoms. If there are new additions then a triggered EQ5D and BODYQ will be asked of the patient via the patient app.

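### The modality comparison uses 12-month change that appears to run from study baseline, although treatments start at different times in that window, so change before a treatment began is attributed to it, with bias in either direction

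*Protocol*

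**What the plan says.** Objective 6 in section 3.1 is "To look at changes in weight and well-being over the time in clinic and whether this is affected by treatment modality". The exploratory row of the section 3.2 outcomes table turns this into "Weight, BMI, EQ5D and Body Q scores changes over 12 months. Comparison of these changes between different treatment modalities", with the objective there worded as covering one year and the timepoints given as "Baseline and every 12 months".

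The Data analysis part of section 4 names multivariable linear regression of that 12-month change as the model. Its stated purpose is "to determine if this is influenced by treatment modality and demographic groups". Neither place ties the start of the 12 months to the start of a treatment.

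The same protocol expects treatments to start at varying times:

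- In section 3.2, Clinical Treatments carry an offer, start, delivery or referral date for each modality. For weight loss drugs the entry is "Y/N if yes which type and when started".
- In section 4, Data collection, clinic staff enter weight and treatments, and "This data entry will be repeated after each clinical visit". Questionnaires are repeated yearly or on a change of treatment.
- In Appendix 2, patients are prompted every 3 months to update treatments: "If there are new additions then a triggered EQ5D and BODYQ will be asked of the patient via the patient app".

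**The concern.** A patient may enter the study, receive diet advice for some months and then start a drug. On the plan's wording, that patient's whole change from baseline to month 12 is the outcome for the drug, including the months before it was taken. This happens even for a newly referred patient with every date recorded. It is a separate matter from patients who were already on treatment when they consented.

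Objective 6 and the fourth point of the Rationale (real-world effectiveness of different interventions, with the new obesity drugs in mind) both rest on this comparison. A reader of the result could not undo the bias, because its size and sign depend on when each treatment started and what happened before it.

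**Working it through.** The protocol gives no weight change, SD, start-time distribution or power calculation for this comparison, so there is no figure of its own to reproduce here. **All rates and start times below are assumptions.** They show the mechanism and its range.

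**1. General form under linear change.** Let a treatment start *s* months after baseline. Let *p* be the rate of weight change before the start, *r* the rate on treatment and *c* the comparator's constant rate, all in kg/month with loss negative.

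- Contrast measured from baseline: p·s + r·(12 − s) − 12c
- Contrast for 12 months on treatment: 12(r − c)
- Difference, measured minus true: s·(p − r)

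The sign depends only on whether earlier loss was slower or faster than on-treatment loss.

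**2. Numbers, with r = −1.**

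| p | c | s = 3 | s = 6 | s = 9 |
|---|---|---|---|---|
| 0 | 0 | −9 of −12 (75%) | −6 of −12 (50%) | −3 of −12 (25%) |
| −0.3 | −0.3 | −6.3 of −8.4 (75%) | −4.2 of −8.4 (50%) | −2.1 of −8.4 (25%) |
| −1.0 | −0.3 | −8.4 of −8.4 (100%) | 100% | 100% |
| −1.5 | 0 | −13.5 of −12 (112.5%) | −15 of −12 (125%) | −16.5 of −12 (137.5%) |
| −1.5 | −0.3 | −9.9 of −8.4 (118%) | −11.4 of −8.4 (136%) | −12.9 of −8.4 (154%) |

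The first two rows are the simple case, in which the patient was on the comparator's course until the start. The last two are the case in which an earlier modality, such as a low calorie diet, was producing faster loss.

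**3. Averaged over starts, simple case.** With starts uniform over the first *S* months and linear accrual, the share shown is (12 − S/2)/12.

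- S = 6: 9/12 = 75%
- S = 12: 6/12 = 50%

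If the effect instead accrues as (1 − e^(−t/4))/(1 − e^(−3)), the averages are 93% and 72%. The dilution therefore depends heavily on the assumed curve.

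**4. Effect of who is escalated.** Simulation of 400,000 patients: background slope with mean −0.25 and SD 0.35 kg/month, a drug adding −1 kg/month from month 6, so a true added change in the window of −6 kg. The contrast is the raw difference in mean baseline-to-12-month change.

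| Who starts the drug | Contrast from baseline |
|---|---|
| Mainly slow losers (probability 0.7 if loss is under 2 kg, else 0.1) | −2.07 kg |
| At random | about −6.0 kg |
| Mainly good responders (probabilities swapped) | −10.3 kg |

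In the first row, counting change from month 6 gives −4.04 kg. Adjusting for change so far as well gives −6.0 kg. So about half of the 3.9 kg gap (6 − 2.07) is change before the start. The other half is the slower background slope continuing afterwards, which is confounding by indication.

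**The case against.** The strongest reply is that this is detail for a statistical analysis plan. The analysis text is one sentence, it does not say how modality is coded or whether it is time-updated, and change from study baseline is read from a timepoint column that also serves as a collection schedule. That inference should be acknowledged. But the protocol does state the outcome, the window, the contrast and the model, and it offers no other anchor. An analysis plan that follows it would inherit the misalignment.

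The second reply is that the comparison is exploratory in a proof-of-concept study. This stands. The primary outcome (clinics using the system) and the secondary outcomes (data capture) are untouched.

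Three stronger readings are tempting and are not supported:

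- A reader might infer that treatment effects are understated in general. The protocol lists modalities that can follow one another, so earlier loss may be faster than later loss, and then the effect is overstated.
- A reader might take −2.07 kg against −6 kg as the size of the problem. That figure comes from an assumed escalation rule that the protocol does not state, and about half of it is a different bias.
- A reader might infer that modalities or clinics will be ranked by how quickly they start treatment. No ranking procedure is specified. The Rationale promises only some insight into interventions and the possible highlighting of service models that work well.

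**Conclusion.** The point holds as misalignment between the outcome window and treatment start. As written, the plan attributes pre-treatment change to the modality, and the resulting bias can go either way. Under linear change it equals s·(p − r): dilution when earlier loss was slower than on-treatment loss, none when equal, overstatement when faster.

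The 75% and 50% figures illustrate the diluted case. They need linear accrual, starts uniform over 6 or 12 months, a pre-treatment course equal to the comparator's, and 12 months on treatment as the effect of interest. The documents supply none of these, so the actual size is unknown.

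The consequence is confined to objective 6 and the effectiveness part of the Rationale. It is worth correcting because the data needed are already in the collection plan.

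**What to change.** In the exploratory row of section 3.2 and in Data analysis:

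1. Keep baseline-to-12-month change for describing the cohort.
2. For the modality comparison, set time zero at the recorded start date of the modality. Take as baseline the last clinic weight on or before that date and the questionnaire triggered by the new treatment. Analyse change over the following 12 months, adjusting for weight at start and change so far.
3. Align comparators at the same time since entry. Alternatively, enter modality as time-updated exposure.
4. Reconcile the window in objective 6 of section 3.1 (the whole time in clinic) with the one-year window in section 3.2.

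The cost is wording and more programming, with no new data items. There are three limits:

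- Fewer patients will have a full 12 months after treatment start. Data collection closes 24 + 6 = 30 months after recruitment opens, so only treatments started by month 30 − 12 = 18 can have it. Time-updated exposure limits this loss.
- Because treatment updates are prompted every 3 months, a triggered questionnaire may be completed after the treatment began. Its date should be compared with the start date before it is used as a baseline.
- Adjusting for weight at start and change so far reduces confounding by indication but does not remove it, and the report should say so.

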#### Objectives of the CORE Study

Our primary objective is to establish a study that will compile data from weight management services, focusing on the following key areas:

1. **Demographics:** Age, sex, socioeconomic status (derived from postcode), ethnicity, marital status and employment status and Job.
2. **Weight History:** Weight at significant life milestones (birth and leaving school), onset of weight issues, highest and lowest adult weight, weight changes over the past five years.
3. **Previous Weight Loss Attempts:** History of interventions and weight loss with these.
4. **Medical Conditions:** List of medical conditions with dates started. Severity of these medical conditions will be assessed using the Kings score and Edmonton score.
5. **Medication:** Details on dosage and frequency and when started on these drugs.

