## 2 RATIONALE

As mentioned above there is very little data on who attends specialist weight management services and how effective the interventions offered in these clinics are. This study will enable us to say

1. Whether there is equal access to treatment based on sex, age, social class and ethnicity and if not start to work out what we can do to ensure this does happen.
2. The characteristics of the people attending the specialist weight management services. This data will give an insight as to how unwell this population is and how many people are being referred to these services which will help with planning of services.
3. How effective these services are and whether this varies from area to area. If we find specific models that are working well we can highlight these to the other clinics.
4. Some insight into the “real world” effectiveness of different types of interventions. This is particularly important with two new obesity drugs now being offered on the NHS.

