## **4 STUDY DESIGN and METHODS of DATA COLLECTION AND DATA ANALYSIS**

### **Study Design**

This is a multicentre observation study of people attending a specialist weight management service. Data will be collected from two sources

1. the patient who is attending the weight management clinic – they will enter data into a phone app called Peoplewith (<http://peoplewith.com>). This will be the primary source of the data.
2. Weight management services - Healthcare professionals or those with delegated access per site will input data into the clinician portal of the peoplewith app. The data entered will be routine data that is already collected in the clinic.

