#### **6.1.1 Inclusion criteria**

1. Patient is willing and able to give informed consent for the participation in the trial.
2. Over the age of 18.
3. Patient, in the investigator's opinion, is able and willing to comply with all the study requirements.
4. Patient is seen in a specialist weight management service across the England and Wales
5. Patient is willing and able to download an application in the English language

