## 7 ETHICAL AND REGULATORY CONSIDERATIONS

**The primary ethical considerations for this study are described below:**

**Consent:** Participation in this study at all sites will require consent. In this study consent will be sought only after the participant has received an information sheet, been given adequate time to consider participation, and had the opportunity to ask the research team any questions they may have. Signed informed electronic consent will be obtained from all participants. The right of the participant to refuse participation without giving reasons will be fully respected. Participants may withdraw from the study at any time, although data already collected will not be withdrawn, as the link to personal data will have been anonymized.

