#### SfE CORE Study Protocol

- Role based privileges are enforced, ensuring only those who require access for their role can access the participant identification key within each site.
- Site login access logs are maintained.
- Data is encrypted at rest when stored in secured databases and in-flight when being transmitted;
  - Encryption protocols implemented throughout the *PeopleWith* platform:
    - Data in-transit: SSL with SHA-256 with RSA Encryption
    - Data at-rest: RSA 2048
    - File Storage (including backups): RSA 2048
- Designated individuals are prompted to renew their password every 90 days.
- Access is revoked upon reappointment, resignation or study completion.
- Technical safeguards implemented throughout including; automatic timeouts (10 minutes), multi-factor authentication, firewalls and intrusion detection systems.

*PeopleWith* acts as the technology partner contracted to the study by the Society for Endocrinology. Under GDPR, *PeopleWith* are the data processor for the study, who provide technology infrastructure to securely manage and store study data. An aggregated, anonymised dataset is made available to and is owned by the Society for Endocrinology. Additionally, *PeopleWith* support onboarding to the technology and deployment to sites, including the implementation of security measurements to protect data. The Society for Endocrinology has undertaken significant technical and information governance due-diligence with *PeopleWith* including the appointment of a Caldicot Guardian. *PeopleWith* is an ICO registered organisation with registration number: ZA745747.

Data held on the app will include:

- Participant Data:
  - Email address, gender assignment, date of birth, postcode brick (i.e. first section), ethnicity and occupation.
- Pseudonymized Data:
  - Study specific participant identification key.
- Health Data:
  - Data entered by participants, such as symptoms, medication adherence, or health outcomes.
- Survey Responses:
  - Data from questionnaires or surveys completed through the app.
- Metadata:
  - Usage data such as timestamps of logins, app interactions, and e-consent verification.
- Study Specific Data:
  - Information explicitly required for research purposes eg weight loss treatment and outcomes

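### The access-disparity outcome is about who reaches the services, but demographic data are planned only for consenting users of an English-language app, so service access and app uptake cannot be separated

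*Protocol*

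**What the plan says.** **The question.** Section 3.2 lists an exploratory outcome to "Assess whether certain demographic groups are underrepresented in specialist weight management services"; objective 7 in section 3.1 has the same aim. The first item of section 2 (Rationale) lists, among the things the study will allow its authors to say, "Whether there is equal access to treatment based on sex, age, social class and ethnicity". In each place the target is the services, not the study sample.

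**The data.** Section 7 (Consent) states: "Participation in this study at all sites will require consent". Inclusion criterion 5 in section 6.1.1 reads: "Patient is willing and able to download an application in the English language". Section 4 says of patient entry in the phone app: "This will be the primary source of the data". Clinicians also enter data, but section 7 (Confidentiality) describes their platform as showing each site its own consented participants. Section 6.2.2 calls the sampling convenience sampling.

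**The analysis.** Section 4 (Data analysis) plans summary statistics "to describe the demographic and clinical characteristics of the people entered into the database". Attenders who do not enrol appear only in the denominator of the capture percentage, as a total.

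**Socioeconomic status.** Section 1 lists "socioeconomic status (derived from postcode" (in brackets in the original). Section 7.6 lists what the app holds, including "date of birth, postcode brick (i.e. first section), ethnicity and occupation"; its data-recording text also refers to the first section of the postcode only.

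**The concern.** To say that a group is under-represented in a service, one needs to know who attends it. The protocol will know this only for attenders who pass three filters: consent, use of a phone app, and use of that app in English. It is plausible that these filters act unevenly by ethnicity, deprivation and age, which are the factors whose access is in question. The documents give no data either way.

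The secondary objective treats 60% capture, with key data on those captured, as giving a fair picture of the clinic population. A capture percentage measures quantity. It says nothing about whether the missing 40% resemble the captured 60%.

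Equal access is the first reason the protocol gives for doing the study. Low uptake could pass for low access, or uneven uptake could hide a real access gap, and the planned data could not show which had happened.

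**Working it through.** **1. The protocol's own enrolment figure (section 6.2.1).** Existing patients 700 × 1.5 = 1,050; new referrals 700 × 2 = 1,400; total 2,450 per service. At 80% capture: 2,450 × 0.80 = 1,960. Over 21 sites: 1,960 × 21 = 41,160. This reproduces. The patient-capture target is 60%, so the illustration uses 2,450 × 0.60 = 1,470 per clinic and 1,470 × 21 = 30,870 overall.

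**2. Observed share when access is equal but uptake differs.** Let *s* be the group's true share of attenders and *r* its uptake divided by that of everyone else. Its share of the database is

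observed = *s r* / (*s r* + 1 − *s*).

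Take *s* = 20% and overall capture 60%. Both *s* and *r* are assumptions; the protocol gives neither.

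| *r* | Uptake, group vs others | Observed share |
|---|---|---|
| 0.9 | 55.1% vs 61.2% | 0.18/0.98 = 18.4% |
| 0.8 | 50.0% vs 62.5% | 0.16/0.96 = 16.7% |
| 0.615 | 40.0% vs 65.0% | 0.123/0.923 = 13.3% |
| 0.5 | 33.3% vs 66.7% | 0.10/0.90 = 11.1% |

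Every row meets the 60% target; for example 0.2 × 0.40 + 0.8 × 0.65 = 0.60. With *s* = 10% the formula gives 9.1% to 5.3% for *r* from 0.9 to 0.5; with *s* = 30% it gives 27.8% to 17.6%.

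**3. Sample size does not help.** At n = 30,870 the standard error of a 20% share is √(0.2 × 0.8 / 30,870) = 0.0023, about 0.2 points. The *r* = 0.8 row is then (0.1667 − 0.20)/0.00228 = −14.6 standard errors from 20%. At one clinic (n = 1,470) it is −3.2. Both ignore clustering by clinic, which would widen the error but leave the bias unchanged.

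**4. What 60% capture alone can say.** If *o* is the observed share and nothing is known about the other 40%, the true share lies between 0.6*o* and 0.6*o* + 0.4. For *o* = 16% that is 9.6% to 49.6%.

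**5. Could later analysis repair this?** A statistical analysis plan can name a comparator population or a weighting method. It cannot supply the demographics of attenders about whom only a total was collected. Section 7.6 requires sites to keep screening logs, but states no demographic content for them and no use in this analysis.

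**The case against.** The strongest reply is that the protocol claims less than this suggests. The outcome is exploratory, objective 7 speaks of exploring potential disparities, objective 5 confines the description to people who enrol, and the primary aim is proof of concept measured by clinic participation. That is fair, and it limits the weight of the point. It does not answer it: objective 7 and the access outcome carry no such restriction, and the Rationale promises a statement on equal access.

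A reader might infer that uptake differences will be reported as unequal access. The protocol does not say how the result will be worded, and neither the size nor the direction of differential uptake is known. What the documents support is that the two cannot be told apart with the planned data.

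A reader might also fold the postcode into the same argument. It is a different problem. A coarse postcode misclassifies socioeconomic status but does not turn app uptake into apparent lack of access. Nor are patients in one postcode area socioeconomically indistinguishable: employment status and job are key variables in section 3.2, and occupation is held on the app. Section 7.6 lists what is held without saying how or when status is derived, and the Data Dictionary named in Appendix 1 is not shown. Derivation from the first section is a reasonable reading, not a stated fact.

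Finally, the uptake ratios are illustrative, and mild ratios give mild distortion. That stands, which is why a range is shown.

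**Conclusion.** The point holds as a limit on what the study can conclude. As the data collection is fixed, the access outcome cannot distinguish low access to the service from low uptake of the app, and reaching 60% capture does not show fair representation. Under the assumed uptake ratios of 0.9 to 0.5, a group that is 20% of attenders would appear as 18.4% to 11.1% of the database with no access disparity at all. The true effect could be smaller or larger, or in the opposite direction. The matter belongs in the protocol because it turns on which data are collected. It affects one exploratory outcome and leaves the primary outcome untouched, so it is a change that should be made, not one on which the study depends.

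The postcode matter is secondary and separate. If only the first section is used, the area measure of socioeconomic status will be coarse for both access (objective 7) and outcome (objective 8) disparities. No size is given here, because the documents contain nothing to anchor one.

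**What to change.** **Main change, in section 4 (Data analysis).** Clinics must already supply an attendance count for the capture formula. Ask for it as aggregate, non-identifiable counts by age band, sex and ethnic group, with deprivation fifth where the clinic has it. Report uptake by group, and base the access comparison on the attender counts, not on the app sample.

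**Fallback.** Where a clinic cannot supply these counts, limit the conclusion in section 2 (item 1) and in the access outcome of section 3.2 to study participants, as objective 5 already does. This is a wording change only.

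**Postcode, as a separate item.** Either derive a small-area deprivation category at registration and store only that category, or state that the area measure is at the level of the postcode's first section and use the employment and occupation data alongside it. The first option means handling a full postcode briefly. That touches the data-minimisation position in section 7.6, so it needs data-protection review and ethics approval. The second needs neither a new data item nor a new data flow.

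**Cost.** A slightly larger extract per clinic, incomplete ethnicity coding at some sites, and ethical approval for the change in data collected, which the protocol already requires under the steering committee's remit. It should be done before data collection is under way.
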